5.3 Method for Assigning Subjects to Treatment Groups

Randomization will be performed by the Pharmaceutical Research Center (PRC) using a scheme designed by the PRC and ICTR statisticians. Subjects will be randomized and stratified based on their baseline use of continuous positive airway pressure (permuted block randomization). Subjects will be classified into the following three categories of baseline CPAP use: 1) < 1 hour per night; 2) between 1 and 4 hours per night; and 3) > 4 hours per night. Subjects not using CPAP will be classified in the < 1 hour per night group. Subjects will be instructed to continue the same CPAP use during the study as they were using at study entry.

5.4 Preparation and Administration of Study Drug

Study drug will be over encapsulated by the University of Iowa Pharmaceuticals (UIP) and stored and distributed by the University of Wisconsin Pharmaceutical Research Center and blinded according to a pre-designed scheme. Subjects will be randomized at the end of visit 1 (screening visit) and will receive study drug at their baseline physiology study visit (visit 3). UIP is an FDA-registered facility compliant with 21 CFR parts 11, 210, and 211, licensed by the DEA to handle controlled substances (Schedules I-V), and capable of handling potent/cytotoxic materials. UIP has been a cGMP facility for over 30 years.

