On a following night, subjects will return to Madison for physiology studies, overnight polysomnography and Holter/heart rate variability measurements*, vascular function measures and control of breathing studies the 2nd night to assess the study drug effects on variables measured at baseline. Subjects will be instructed not to consume caffeine (both solid and liquid forms) after midnight the night before they are admitted to the CRU and after 8pm on night 1. Subjects may consume caffeine after the physiology study on Day 1 and before 8pm on Day 1. Subjects will also be instructed not to smoke after 10 pm once they are admitted to the CRU until discharged. Subjects will not be allowed to participate in the study if they are unable to refrain from smoking after 10 pm for up to 24 to 48 hours once they are admitted to the CRU until discharged.

*Holter and Heart rate variability measurements are optional and will only be offered to UW subjects. They can choose to opt-in or opt-out of those procedures. Subjects who are non-CPAP users will have Holter monitoring done at Visits 3 and 6, but will not have Holter monitoring performed at Visits 2 and 5. The Holter monitors will be connected by UW Sleep Laboratory Technicians or study team personnel. Subjects may disconnect the Holter monitor on their own, or they may come back to UW-Madison to have the Holter monitor removed. A postage-paid envelope will be provided to subjects to return to Holter monitor by mail.

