3.2 Primary Study Endpoints

The primary outcome variable is the difference in the individual slope of the MSNA – SaO₂ response curve at 6 weeks and baseline between treatment groups. Basal normoxic MSNA and MSNA responses during hypoxia will be compared between the three treatment groups. For purposes of quantification, MSNA is expressed as burst frequency (bursts/min), burst amplitude (arbitrary units) and total minute activity (burst frequency x mean burst amplitude). Total minute activity of mSNA is an effective way to capture the change in both burst frequency and burst amplitude. Both amplitude and burst frequency are influenced by disease states such as OSA and by environmental conditions such as hypoxia. Postganglionic mSNA in the right peroneal nerve will be recorded directly using the microneurography technique (95). The neural signals are passed to a differential preamplifier, an amplifier, a band-pass filter, and an integrator (time constant=100 ms). Placement of the recording electrode within a muscle nerve fascicle is confirmed by the presence of muscle twitches in response to electrical stimulation, the appearance of afferent activity in response to tapping or stretching of muscle, but not gentle stroking of skin, in the appropriate receptive fields, and other criteria. Once an acceptable neural recording (signal-to-noise ratio >3:1) is obtained, the subject is instructed to maintain the leg in a relaxed position for the duration of the study. Sympathetic bursts will be identified by computer-assisted inspection of the mean voltage neurogram.

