5.6.1 Pregnancy Testing and Birth Control

Women of child-bearing age are eligible subjects for this study. However, since study drugs are pregnancy rate "D" (losartan) and "C" allopurinol, female subjects will take a urine pregnancy test at Visit 1 to ensure they are not pregnant. A urine pregnancy test will be repeated at Visit 1A if the study visit occurs more than 90 days after Visit 1. Furthermore, a urine pregnancy test will also be given at Visit 3 prior to study drug dispensing. The Pregnancy and birth control case report form should be completed at Visit 1, Visit 1A (if applicable) and Visit 3. On this case report form the method of birth control used should be documented and subjects are instructed to keep their birth control consistent throughout the study. Methods of birth control that are acceptable while participating in this study include oral contraceptives, hormonal contraceptives, hormonal implants, contraceptive patches, NuvaRing, intrauterine device hormonal, intrauterine device non-hormonal, barrier method, spermicide, post-menopausal for greater than or equal to two (2) years, tubal ligation, bilateral oophorectomy, or hysterectomy, vasectomy, or abstinence. If a female is practicing abstinence, she should confirm this, including duration, and initial and date the case report form.

5.7 *Blinding of Study Drug*

Allopurinol and Losartan tablets will be over encapsulated and dispensed to subjects with a placebo using a double-dummy design. Both subjects and investigators will be blinded to study drug assignment. The PRC will have unblinding information should the need arise to unblind a subject's study drug assignment. To obtain unblinding information, please call the University of Wisconsin Pharmaceutical Research Center at [contact].

5.8 *Receiving, Storage, Dispensing and Return*

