6.2 Summary of Visits

Subjects may complete some, but not all procedures without a protocol deviation occurring or affecting their study eligibility. For logistical or other reasons, subjects may complete some of the procedures (but not all procedures) (i.e. in cases of non-exclusionary subject disabilities that preclude them from having certain procedures done or body habitus that does not allow completion of certain procedures.). Reimbursement for participation will be pro-rated for Visits 3 and 6 as in protocol section 11.2.

Visit 1: Screen Visit (will be performed at each respective recruitment site)

- informed consent, height and weight, heart rate, blood pressure, temperature, and electrocardiogram recorded, blood samples, urine pregnancy test, brief history (performed by study coordinator and local PI)
- physical examination (local PI and UWHC medical staff (i.e., physician, physician's assistant, or nurse practitioner) for Madison subjects)

Visit 1A: If visit 2 will occur more than 90 days after visit 1, subjects will undergo repeat screening procedures in a separate visit to the local study site (Visit 1A) including:

Medical history, medication history, birth control assessment, blood samples, urine pregnancy test, AE assessment, electrocardiogram recorded (performed by the local PI, study coordinator, or medical staff (i.e., physician, physician's assistant, or nurse practitioner)

Visits 2 and 5: Home Blood Pressure Monitoring (will be performed at each local site where subjects were originally enrolled)

- Receive blood pressure monitor and Holter/heart rate variability monitor* to wear for 24 hours along with the diary recording of activity each time they engage in activity and each time the blood pressure cuff inflates; subject returns to the study site the following day (all activities performed by coordinator-local PI consulted if necessary). Subjects at UW-Madison will come to the School of Pharmacy Clinical research space of the Office of Clinical Trials Examination Space (H6/136 CSC) to be set up with their 24-hour blood pressure cuff and Holter/heart rate variability monitor. Adverse events will be assessed at visits 2 and 5.

Version: 23, 7-25-17

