*Holter and Heart rate variability measurements are optional and will only be offered to UW subjects. They can choose to opt-in or opt-out of those procedures. Subjects who are non-CPAP users will have Holter monitoring done at Visits 3 and 6, but will not have Holter monitoring performed at Visits 2 and 5." The Holter monitors will be connected by UW Sleep Laboratory Technicians or study team personnel. Subjects may disconnect the Holter monitor on their own, or they may come back to UW-Madison to have the Holter monitor removed. A postage-paid envelope will be provided to subjects to return to Holter monitor by mail.

Visits 3 and 6: (each visit requiring a one or two night stay in Madison at the CRU at UW and the VA Hospital for all subjects enrolled in the study)

- Day 1: Vital signs, Heart Rate; Forearm Blood Flow; Blood Samples; Cerebral blood flow; Nerve activity; Reduced oxygen exposure and increased oxygen breathing; overnight sleep study and heart rhythm measurements at the CRU to measure brain waves, respiration, blood oxygen level, snoring, leg movements, heart rhythm, and heart rate variability* (performed by PIs and sleep technician). A physical exam will also be obtained. If bruit are noted on physical exam the subject will no longer be able to participate in the study. The presence of a bruit would potentially indicate previously unrecognized cardiovascular disease.

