6.3 Sample collection

Blood samples collected during Visits 1 and 4 will be processed for the specific laboratory parameter at the local site and assayed in the clinical labs (or couriered from LaCrosse to Marshfield to be assayed). Samples will be collected and sent to the clinical laboratory for measurement of serum creatinine, serum potassium, serum glucose, lipid panels, serum uric acid, etc. At Visits 3 and 6 at UW-Madison, blood samples will be drawn at rest while the subject is breathing room air. Uric acid will be collected and assayed in the UW Hospital and Clinics Clinical Laboratory and other samples will be collected for research use. These samples collected for research use will be centrifuged, aliquoted, and stored in the locked freezer space at the University of Wisconsin School of Pharmacy for future assay. Stored blood samples will be stripped of identifiers and only labeled with study subject number and Visit number. Plasma will be sent to the TTR Analytical Laboratory Core at the University of Iowa College of Pharmacy for plasma catecholamine measurement. Other plasma will be assayed at the UW School of Pharmacy for oxidative stress markers.

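### Does randomising at the end of Visit 1, before the Visit 3 checks, the baseline MSNA recording and the first dose, undermine the primary comparison?

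*Combined protocol and SAP*

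**What the plan says.** Section 5.4 states: "Subjects will be randomized at the end of visit 1 (screening visit". Section 3.1 gives the same order: screening, randomisation, then the Visit 3 baseline study. Sections 4.3 and 5.5 withhold study drug until the end of Visit 3.

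Several steps fall between allocation and the first dose:

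- Section 6.2, Visit 1A: "If visit 2 will occur more than 90 days after visit 1, subjects will undergo repeat screening procedures".
- Section 6.2, Visit 3 physical examination: "If bruit are noted on physical exam the subject will no longer be able to participate in the study".
- Section 5.6.1: "a urine pregnancy test will also be given at Visit 3 prior to study drug dispensing".
- Section 3.1, smoking: "Subjects will not be allowed to participate in the study if they are unable to refrain from smoking after 10 pm".
- Section 3.2, the MSNA measurement, which proceeds "Once an acceptable neural recording (signal-to-noise ratio >3:1) is obtained".

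Section 6.2 also accepts partial completion: "Subjects may complete some, but not all procedures without a protocol deviation occurring or affecting their study eligibility".

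Section 7.1 enrols 120 to randomise 100 and bases its power on complete MSNA slope data from 20 subjects per group. Section 7.3 adopts an intent-to-treat philosophy, compares deletion of subjects with missing data against last observation carried forward (LOCF), and says drop-outs are covered by the sample size. It does not mention subjects who were randomised but never dosed, or who have no baseline slope.

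**The concern.** Allocating after eligibility is settled and just before treatment keeps the randomised set and the analysed set close together. Here eligibility is still open at allocation. A bruit, a positive pregnancy test or a Visit 1A result can end participation afterwards. Visit 1 laboratory results might also arrive late: turnaround is not stated, and section 6.3 says samples are "assayed in the clinical labs (or couriered from LaCrosse to Marshfield to be assayed". The primary outcome is a change from a baseline that has not yet been measured, and microneurography does not always give a usable signal.

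Three things then seem to be at stake:

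- Section 7.3 has no rule for these subjects. LOCF has nothing to carry forward without a baseline, and it assigns a change of zero to a subject who has a baseline but no later value.
- The one numerical drop-out allowance, 120 to 100, is used up before randomisation.
- The balance given by CPAP-stratified blocks need not carry over into the analysed set.

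**Working it through.** **Inputs.** From section 7.1: 120 enrolled, 100 randomised, 20 completers per group, difference 3.07 (1.13 vs −1.94), alpha 0.017, power 90%. Assumed, because the documents give no rates: pre-dose loss of 5%, 10% or 20%, and 85% retention after dosing.

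**1. The plan's own figures.** The enrolment allowance is 1 − 100/120 = 16.7%, all before randomisation. The interim SD behind the 90% power is not stated, so that figure cannot be reproduced from its inputs. It can be solved for the SD. Taking alpha as two-sided, with a normal approximation:

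SD = 3.07 / [(2.387 + 1.282) × √(2/20)] ≈ 2.65.

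Section 7.1 also quotes an SD of 8–10 for slope from earlier laboratory data. How that fits with 2.65 is a separate question and does not bear on when subjects are randomised.

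**2. Room for loss after randomisation.** Needed: 3 × 20 = 60. Randomised: 100. Margin: 1 − 60/100 = 40%.

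**3. Evaluable number under each timing, with enrolment fixed.**

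- 10% pre-dose loss: 100 × 0.90 × 0.85 = 76.5 whether allocation comes before or after that loss. If every pre-dose loss were removed before allocation, the share lost after randomisation would fall from 1 − 0.765 = 23.5% to 15%. That changes the denominator, not the information.
- 20% pre-dose loss: 100 × 0.80 × 0.85 = 68, still above 60.

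**4. Arm sizes.** Start from 33 per arm and remove 5, 10 or 20 of 99 at random. By simulation, the chance that the largest and smallest arms differ by 4 or more is 12%, 33% or 54%. The cost for two arms of 28 and 32 instead of 30 and 30 is

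√(1/28 + 1/32) / √(2/30) = √(0.06696 / 0.06667) = 1.002,

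about 0.2% on the standard error. Ordinary later drop-out causes the same thing. With 10% pre-dose loss and 85% retention, the chance of a spread of 4 or more in the final set is about 57% with Visit 1 allocation and still 41–44% with Visit 3 allocation.

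**5. LOCF.** If a fraction f of each arm has a baseline but is never dosed, its carried-forward change is zero and the difference becomes 3.07 × (1 − f): 2.92, 2.76 and 2.46 for f = 5%, 10% and 20%. However, f is not the whole pre-dose loss. Section 6.2 puts MSNA on day 1 of Visit 3 and dispensing on day two, so only subjects lost between those points count. Visit 1A losses come before the recording, and a failed recording leaves no baseline at all. A fraction of 20% is not plausible for that group. LOCF also gives a zero change to anyone with a baseline who drops out after dosing, whenever allocation took place.

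**6. Bias.** Section 5.7 blinds subjects and investigators. Before the first capsule no treatment effect can drive withdrawal, so the loss should be independent of arm.

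**The case for a change.** The best opposing case is about discipline rather than bias or power. A plan that claims intent to treat should say who is in the primary set. Without a baseline, both options in section 7.3 reduce to deletion, which sits awkwardly with that claim, and a set left undefined can be chosen after the data are seen. The pharmacy centre both randomises (section 5.3) and dispenses at Visit 3 (section 5.8.2), so later allocation would use existing roles.

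Part of this stands. Section 7.3 is silent on these subjects, and it does not say which of its two options leads. A sentence on the point would be tidy. The room for choice is small, though. Whether a subject has a baseline slope is a recorded fact, fixed before dosing and under blind, and section 7.2 has the analysing statistician blinded to drug. Section 7.3 already commits to summarising reasons for drop-out.

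The argument for moving allocation is weaker. Because section 6.2 accepts partial completion, a usable recording could not sensibly be made a condition of entry. Subjects without a baseline would still be randomised, and block balance would still not be assured in the analysed set. Some of the listed events are also uncertain: smoking can be asked about at screening, Visit 1A arises only after a gap of more than 90 days, and late laboratory results are conjecture. At Version 23, after an interim analysis and a reduction in sample size, the change would leave the trial with two allocation schemes to describe.

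**Conclusion.** The concern describes the sequence correctly but does not call for a change. Losses before dosing and under blind leave the comparison of observed changes unbiased. Fixed enrolment gives the same evaluable number with either timing, 76.5 under the 10%/85% assumptions. The 40% margin between 100 randomised and 60 completers absorbs even the 20% case, which leaves 68. Unequal arms of the size illustrated cost about 0.2% in standard error. LOCF dilution is confined to a sensitivity comparison and to the few subjects recorded on day 1 of Visit 3 and not dosed on day two.

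What remains is a gap in section 7.3 that an analyst fills in the obvious way: the primary comparison uses randomised subjects whose change in slope can be computed, pre-dose losses are reported by arm with the other drop-outs, and LOCF is not attempted where there is nothing to carry forward. Following the plan as written still gives a sound primary result on this point.

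This rests on the blind holding until the first dose and on the assumed loss rates. On the count of completers alone, loss from all causes after randomisation would have to exceed 40% before the total fell below 60.

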5.5 Subject Adherence Monitoring

All subjects will receive instructions on how to take and record medication adherence in a diary. Subjects will not receive study medications until the end of the Physiology Visit in Madison (Visit 3) and will be instructed to bring their study medications with them to Visit 4 (two weeks after starting medication at local study site) and Visit 6 (Six weeks after starting study medication – in Madison). Serum uric acid concentrations and plasma renin activity will be measured at baseline and after 6 weeks of study medication and will provide an indirect measure of drug adherence in subjects receiving allopurinol and losartan. Adherence to CPAP therapy will be monitored at Visit 4 (two weeks after starting medication) and Visit 6 (Six weeks after starting study medication). CPAP adherence can be determined from the electronic data card in the CPAP machine and downloaded into a printable report. Each site will have a card reader and software for

Version: 23, 7-25-17

downloading the information from subjects' CPAP machines at Visit 4. Subjects on BiPAP will use their machines instead of ours, and we will attempt to get their adherence data from them.

5.5.1 CPAP Before and During Study

Subjects who are using CPAP or BiPAP prior to the study will be asked to provide adherence data for the time period prior to them entering the study. Subjects who require CPAP or BiPAP must be on treatment for a minimum of 3 months prior to Visit 2. This information will be obtained from their CPAP/BiPAP machine or from their home health provider that services their CPAP/BiPAP machine. We will also ask for their permission to contact their sleep physician to obtain a copy of their sleep study report. This will help us to determine how severe their sleep apnea is. Consent to obtain this information from home health providers and sleep physician will be obtained in the informed consent document. Subjects who qualify for the study will be instructed to continue to use CPAP/BiPAP the same amount during the study as they were using prior to the study. If subjects are not using CPAP/BiPAP prior to study entry, they will be instructed to continue not using CPAP/BiPAP during the study.

At Visit 3, subjects will be given a CPAP machine or CPAP compliance card to use during the study. Subjects using BiPAP will continue to use their own BiPAP machine. We will set the pressure on this machine to the same pressure the subject was using on their machine at home. Subjects will bring their CPAP/BiPAP machine or compliance card with them to Visit 4 (at local site) and Visit 6 (in Madison) to have the adherence data checked. Investigators should remove the compliance card from the CPAP machine and download the data at Visits 4 and 6. After the download, the cards should be returned to the subjects' CPAP machines. Subjects will use the mask they had previously been using with the CPAP/BiPAP machine issued to them. The Respiration CPAP machines given to subjects during the study will be capable of measuring residual breathing events to determine how effectively the machine is treating a subject's sleep apnea.

